6. DATA CONVENTIONS

The following analysis conventions will be used in the statistical analysis.

6.1. Definition of Baseline for Efficacy/Safety Variables

Unless otherwise specified, the Baseline assessment for all measurements will be the latest available valid measurement taken prior to the administration of investigational product.

If the scheduled Baseline Day 1 measurements are not available, screening assessments may be used.

6.2. Data Handling Convention for Efficacy Variables

Algorithm for Calculation of Area Under the Curve (AUC)

The AUC for the FEV1, TNSS, and TOSS for each Cat Allergen Challenge will be calculated using the trapezoidal rule. For each patient at each EEU visit, the AUC will be calculated over the time period of 0 to 2 hours. For example, the AUC will be calculated using the formula:

$$AUC_{[0-2\ hr]} = \left[\sum_{i=1}^{12} (t_i - t_{i-1}) * (D_i + D_{i-1})/2 \right] / (t_{12} - t_0)$$

Where

- D_i is the FEV1, TNSS or TOSS value obtained at time t_i
- t_i is the time (in hours) for which D_i is measured, such as $t_0 = 0$, $t_1 = 1/6$ hour, $t_2 = 2/6$ hour, $t_3 = 3/6$ hour, $t_4 = 4/6$ hour, ..., $t_{12} = 2$ hours.

If the patient remains in the EEU for less than 2 hours, LOCF will be used to impute values out to 2 hours. In the case of missing FEV1 measurements at one or more time points at a visit while the patient is in the EEU, linear interpolation will be used to impute missing values.

Additional analyses will be performed where the LOCF will be used to impute values out to 4 hours, where i ranges from 0 to 24. Also, the AUC will be calculated over the time while the patient is in the EEU, where the maximum value of i corresponds to the timepoint of the last spirometry effort performed in the EEU to provide the average FEV1 value during EEU exposure.

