2.2. Sample Size and Power Considerations

The primary objective of this study is to assess the time to EAR in a Controlled Cat Allergen Challenge in patients receiving REGN1908-1909 compared to placebo-treated patients. Patients will be randomized (1:1) to receive placebo or REGN1908-1909. With 30 patients per treatment arm, an increase in median time to EAR from 58 minutes in the placebo-treated patients to 132 minutes in patients treated with REGN1908-1909 (ratio of median duration of tolerated exposure of 2.25 or, equivalently, hazard ratio of 0.44) can be detected with 84% power assuming a one-sided type I error of 0.05 and a 13% dropout rate (8 patients). A median time to EAR of 58 minutes was observed in untreated patients in the Alyatec validation study ([Gherasim, 2018](#)) and the ratio of median duration of tolerated exposure of 2.25 is based on the estimated effect size of Omalizumab observed in a previous Cat Allergen Challenge study performed in a live cat room ([Corren, 2011](#)). These estimates of drug effect from this live cat room challenge provide the closest data available for powering this study, as an interventional study has not previously been performed in an EEU with cat allergen. The sample size calculation was performed based on the log-rank test comparing the duration of tolerated exposure of 2 groups with the above-mentioned assumptions.

With 60 cat-allergic patients, this study also has 88% power to detect differences in the key secondary endpoint, percent change in the AUC of FEV1 induced by a Controlled Cat Allergen Challenge over the exposure interval from baseline to the Controlled Cat Allergen Challenge in patients treated with placebo as compared to REGN1908-1909. This power calculation assumes a mean AUC of 27 in the placebo-treated patients compared to 15 in patients treated with drug, based on a previous Cat Allergen Challenge study and a one-sided type I error of 0.05 ([Corren, 2011](#)). The primary analysis will be conducted on the full analysis set (FAS) population (Section 3.1).

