5.6.1. Analysis of Primary Efficacy Variable(s)

The time to EAR for each treatment will be examined using Kaplan Meier estimates with patients being censored at 4 hours if they did not experience an EAR and remained in the EEU for 4 hours. If a patient leaves the EEU before experiencing an EAR and for reasons unrelated to their clinical symptoms, they will be censored at the time of EEU departure. The median time to EAR for each treatment group and the corresponding 95% confidence intervals will be presented for each Controlled Cat Allergen Challenge. A formal comparison of time to EAR in the treatment groups at day 8 will be performed using a Cox proportional hazards model, adjusting for allergen concentration in the EEU and time to EAR in the baseline Cat Allergen Challenge. In patients who receive EEU related medications (including medications given on-site and rescue medications taken at-home), the impact of the carryover of medications between challenges will be explored by including taking medication or not as baseline variable for the model of each subsequent visit. A one-sided 5% statistical test of the hazard ratio for placebo compared to drug will be performed.

If the Cox proportional hazards model does not converge, an extension of the Wilcoxon Rank Sum test comparing the ranks of time to EAR under censoring, adjusted by the covariates specified above, will be used ([LaVange and Koch, 2006](#)). As an additional sensitivity analysis, the presence or absence of an EAR within the 4-hour period in the REGN1908-1909 treatment group as compared to placebo will be tested using a Fisher's Exact Test.

Subgroup analyses may be performed by gender, age, baseline IgE and the ratio of Fel d 1 IgE to Cat Allergen IgE at baseline. The ratio of Fel d 1 IgE to Cat Allergen IgE at baseline (log transformed if the distribution is skewed) will also be explored as potential covariate in the Cox proportional hazards model.

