10. APPENDIX

10.1. Summary of Statistical Analyses

Efficacy Analysis:

Endpoint	Analysis Populations	Primary Analysis	Statistical Method	Supportive Analysis	Subgroup Analysis	Other Analyses
Primary Endpoint						
Time to EAR	FAS, PPS	Time to EAR (a 20 % drop in FEV1 or when the subject exits the EEU on day 8 due to clinically significant symptoms), censored at 4 hours if the patient does not experience an EAR	Cox proportional hazards model	Yes Kaplan Meier estimates and plots	No	Sensitivity Analysis: Fisher's exact test comparing the proportion of subjects with EAR
Secondary Endpoints						
Time to EAR	FAS, PPS	Time to EAR (a 20 % drop in FEV1 or when the subject exits the EEU on days 29, 57, and 85 due to clinically significant symptoms), censored at 4 hours if the patient does not experience an EAR	Cox proportional hazards model	Yes Kaplan Meier estimates and plots	No	Sensitivity Analysis: Fisher's exact test comparing the proportion of subjects with EAR
AUC of FEV1	FAS	Percent change in the AUC of FEV1 from baseline to days 8, 29, 57, and 85	MMRM	No	No	No
AUC of TNSS	FAS	Change in the AUC of TNSS from baseline to days 8, 29, 57, and 85	MMRM	No	Yes	No

Endpoint	Analysis Populations	Primary Analysis	Statistical Method	Supportive Analysis	Subgroup Analysis	Other Analyses
AUC of TOSS	FAS	Change in the AUC of TOSS from baseline to days 8, 29, 57, and 85	MMRM	No	Yes	No
Cat allergen quantity	FAS	Change and percent change in cat allergen quantity as experienced by patients from baseline to days 8, 29, 57 and 85	MMRM	No	No	No

Safety Analyses:

Endpoint	Analysis Populations	Primary Analysis	Statistical Method	Supportive Analysis	Subgroup Analysis	Other Analyses
Adverse Events	FAS	Percent of patients by system organ class	Descriptive Statistics	No	No	No

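### The LOCF rule for the AUC and the Fisher test of EAR have no provision for patients who leave the EEU early for non-clinical reasons, although the primary model censors them

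*SAP*

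**What the plan says.** SAP 5.6.1 foresees patients who leave the EEU before an EAR; when they do so "for reasons unrelated to their clinical symptoms, they will be censored at the time of EEU departure". Protocol 10.4.3.1 has the same rule, and Protocol 5.1 lets patients leave the unit whenever they wish.

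The AUC rule in SAP 6.2 does not look at why the patient left: "If the patient remains in the EEU for less than 2 hours, LOCF will be used to impute values out to 2 hours". An additional analysis extends the carry-forward to 4 hours. SAP 5.6.2 makes the 0 to 2 hour LOCF version the primary AUC method for FEV1, TNSS and TOSS; SAP 2.2 calls the FEV1 AUC the key secondary endpoint.

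As a sensitivity analysis of the primary endpoint, SAP 5.6.1 states that "the presence or absence of an EAR within the 4-hour period in the REGN1908-1909 treatment group as compared to placebo will be tested" with Fisher's test. SAP 10.1 lists "Fisher's exact test comparing the proportion of subjects with EAR" for day 8 and also for days 29, 57 and 85. Neither place says how a patient censored before 4 hours is classified. The SAP 10.1 rows also describe censoring at 4 hours for anyone without an EAR, omitting the condition in 5.6.1 that the patient stayed the full 4 hours.

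SAP 6.3 refers missing efficacy data to Sections 4.5.1 and 4.5.2. Neither covers early non-clinical departure.

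**The concern.** LOCF is reasonable after an EAR or a symptom-driven exit, because the value carried forward is the reaction. After a non-clinical exit it is whatever FEV1 or symptom score preceded the reaction. Every randomized patient had a fall of at least 20% in the baseline challenge (Protocol 6.2.1), so the baseline AUC contains a reaction. The change from baseline then compares that reaction with a pre-reaction value and shows an improvement that was not observed.

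In Fisher's test, a patient who left after 20 minutes without an EAR has not been shown to be EAR-free for 4 hours. Counting that patient as EAR-free treats unobserved time as protection. At stake are the main analysis of the key secondary endpoint, the nasal and ocular AUCs, and the binary check on the primary result.

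**Working it through.** **Planning figures.** "With 30 patients per treatment arm", SAP 2.2 assumes "an increase in median time to EAR from 58 minutes in the placebo-treated patients to 132 minutes in patients treated with REGN1908-1909", with one-sided 5% error and 8 dropouts, leaving 26 per arm. With exponential times and censoring at 240 minutes, the chance of an EAR by 4 hours is 1 - 2^(-240/58) = 0.943 on placebo and 1 - 2^(-240/132) = 0.716 on drug (0.717 at HR 0.44). Expected events are 26 × (0.943 + 0.717) = 43.2. Schoenfeld power at HR 0.44 is Φ(√43.2 × |ln 0.44| / 2 - 1.645) = 0.854; at HR 1/2.25 it is 0.847. The stated 84% is reproduced and is not in dispute.

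**AUC.** Assume FEV1 starts at 3.0 L and falls linearly to -20% at 60 minutes. If the patient leaves at L minutes (L ≤ 60), the fall at exit is f = 20 × L/60 percent. The SAP 6.2 trapezoid with LOCF to 2 hours gives a mean fall of f × (1 - L/240).

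| Exit | f | LOCF AUC vs start | AUC (L) | Change vs a baseline AUC of 2.550 L |
|---|---|---|---|---|
| 60 min, EAR | 20% | -15.0% | 2.550 | 0% |
| 50 min, non-clinical | 16.7% | -13.2% | 2.604 | +2.1% |
| 30 min, non-clinical | 10% | -8.8% | 2.738 | +7.4% |
| 10 min, non-clinical | 3.3% | -3.2% | 2.904 | +13.9% |
| Never falls | 0% | 0% | 3.000 | +17.6% |

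The last column divides each AUC by 2.550, the baseline value if the same path ran to EAR. All rows but the last are the same patient with an unchanged reaction.

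The planned sensitivity analyses do not remove this:

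- LOCF to 4 hours gives f × (1 - L/480): -3.3% for the 10-minute leaver against -17.5% at EAR.
- The average over time actually spent in the EEU is f/2: -1.7% against -10%. It uses no LOCF but still sees only the pre-reaction period.

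**Fisher's test.** Simulation with 30 per arm, 10,000 runs, a one-sided 5% test, and non-clinical leavers departing uniformly over 0 to 240 minutes. A leaver whose EAR comes first counts as an EAR. Entries are rejection rates.

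| Leavers, placebo / drug | Medians 58/132: counted EAR-free | Excluded | Null 58/58: counted EAR-free | Excluded |
|---|---|---|---|---|
| 0 / 0 | 0.659 | 0.659 | 0.005 | 0.005 |
| 4 / 4 | 0.592 | 0.604 | 0.010 | 0.004 |
| 0 / 4 | 0.772 | 0.580 | 0.028 | 0.006 |
| 4 / 0 | 0.463 | 0.677 | 0.002 | 0.007 |
| 0 / 8 | 0.866 | 0.501 | 0.085 | 0.005 |

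Earlier exits sharpen the pattern. With 26 per arm and exits uniform over the first hour, power is about 63% with no exits. With 10% exits in each arm it is about 49% counted and 55% excluded. With 10% in placebo only it is about 32% against 60%, and in drug only 79% against 57%. Under the null with 15% exits in drug only, counting leavers as EAR-free rejects in about 16% to 17% of trials.

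**The case against.** **Full protection.** A reader might infer that both analyses score early leavers as fully protected. For the AUC this is wrong: LOCF keeps any fall or symptoms present at exit, and only a patient with no response at exit scores 0%. For the same reason, spreading the planned placebo mean of 27 over 26 patients (27/26 = 1.04 lost per leaver) is an upper bound. It also applies the protocol's AUC of percent change to a SAP endpoint based on the AUC of FEV1 in litres.

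**Fisher scoring.** Counting leavers as EAR-free is the literal reading, not a written rule. SAP 6.3 leaves missing categorical data out of percentages, and the FAS requires a completed day 8 challenge (SAP 3.1, where completion is undefined), so exclusion is conceivable. But a recorded absence of EAR is not plainly missing, and if the FAS removed early leavers, the censoring rule in SAP 5.6.1 would have nothing to act on at day 8. The FAS condition also does not address the later challenges. The rule is unspecified.

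**Direction and power.** A reader might infer that the drug effect always shrinks, or that the whole loss of Fisher power comes from the scoring. Neither holds. Drug-only exits raise the rejection rate. In the 10%-per-arm case about 8 of the 14 points lost (63% to 55%) are lost information that exclusion does not recover; about 6 (55% to 49%) are scoring.

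**Mitigation.** The main AUC ends at 2 hours, so later exits do not affect it. Planned Kaplan-Meier estimates already censor these patients correctly. Secondary p values are nominal. These points limit the stakes but do not supply the missing rule.

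**Conclusion.** The concern holds in limited form and should be fixed. SAP 6.2 carries forward pre-reaction values for patients whom SAP 5.6.1 recognises and censors. In the worked path this turns a true -15.0% into anything from -13.2% (exit at 50 minutes) to -3.2% (exit at 10 minutes). Fisher's test lacks a rule; on the literal reading, balanced exits spread over the 4 hours hardly matter (0.592 counted against 0.604 excluded), but unbalanced ones can mislead in either direction and can push null rejection above 5%.

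The primary Cox test is unaffected. The documents give no non-clinical exit rate, so the practical size is unknown and is nil if nobody leaves early. The figures assume exponential EAR times, the stated exit patterns, a one-sided Fisher test (the SAP does not state sidedness) and a linear FEV1 path.

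**What to change.** - **SAP 6.2:** apply LOCF only after exit for an EAR or for clinically significant symptoms. For any other exit before 2 hours (before 4 hours in the additional analysis), set that visit's AUC to missing and leave it to the MMRM planned in SAP 5.6.2.
- **SAP 5.6.1 and 10.1:** replace Fisher's test with a comparison of Kaplan-Meier EAR-free proportions at 4 hours, or exclude from Fisher's test patients censored before 4 hours. Kaplan-Meier is preferable because it uses the time observed. Exclusion drops leavers without an EAR but keeps those who reacted first, which leaves a small bias: a null difference in EAR proportions of -0.011 with 8 drug-only leavers, against 0.072 if they are counted EAR-free.
- **SAP 10.1:** align the censoring description with SAP 5.6.1.

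The cost is a few sentences and a small programming change. The reason for exit is already needed for the primary censoring rule. The downside is that a few visit-level AUCs become missing and rely on the MMRM's missing-at-random assumption, which is plausible for exits unrelated to symptoms.

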6.3. Data Handling Convention for Missing Data

Rules for handling missing data for primary and secondary efficacy variables are described in Section 4.5.1 and Section 4.5.2.

For categorical variables, patients with missing data are not included in calculations of percentages unless otherwise specified. When relevant, the number of patients with missing data is presented.

To determine whether a medication is prior or concomitant, the missing medication start date is estimated as early as possible up to randomization date, and the missing medication end date is

estimated as late as possible. If the medication start date is missing, the onset day will not be imputed in medication listings.

If a baseline value is missing for an efficacy endpoint, the patient will be excluded from analyses involving a change or percent change from baseline.

Adverse event

If the intensity of a TEAE is missing, it will be classified as “severe” in the frequency tables by intensity of TEAEs. If the assessment of relationship of a TEAE to the investigational product is missing, it will be classified as related to the investigational product.

6.4. Data Handling Conventions for Biomarker Data

The following analysis conventions will be used in the statistical analysis:

- a) The baseline measurement will be the last measurement prior to dosing. If patients are missing baseline data, the values obtained at screening will be used.
- b) For data points above ULQ (e.g. for results reported as >XX), the ULQ plus one significant digit will be used.
- c) For data points below LLQ (e.g. for results reported as <XX), 0.5X the LLQ will be used.

6.5. Visit Windows

Data analyzed by visit (including efficacy, laboratory data, vital signs, and ECG) will be summarized by the study scheduled visits described in the study protocol and SAP, “Schedule of Events”. The analysis visit windows will be exhaustive so that all available values obtained from unscheduled visits, early termination (ET) visit and end of treatment (EOT)/end of study (EOS) have the potential to be summarized.

6.6. Unscheduled Assessments

The determination of baselines and values at the end of treatment for both efficacy and safety variables will be based on scheduled available assessments and unscheduled available assessments.

Extra assessments (laboratory data or vital signs associated with non-protocol clinical visits or obtained in the course of investigating or managing adverse events) will be included in listings, but not summaries except for the endpoint determination. If more than one laboratory value is available for a given visit, the first observation will be used in summaries and all observations will be presented in listings.

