8. Titrated SPT with Serial Allergen Titration with cat allergen will be performed at screening visit 3, days 29, 85, and 113. On days when an allergen challenge is performed, the test will be performed prior to allergen challenge.
9. FeNO is assessed during screening, Visit 4 and then 24 hours after EEU exposure at day 30 and day 86.
10. All safety assessments performed at screening have to be normal and checked against the inclusion/exclusion criteria prior to REGN1908-1909 administration on day 1 (baseline).
11. On day 1, vital signs are taken prior to PK draw, prior to REGN1908-1909 administration, and at 2 hours ( $\pm 10$  min) after completion of the injection.

12. Vital signs are taken prior to entry into the EEU, at exit from the EEU, and prior to leaving the clinical trial unit, and any additional times as needed.
13. Telephone call to collect AEs and concomitant medications, including any medications used from the rescue treatment kit, up to 24 hours after the EEU exposure.
14. Total blood draw at any visit will never exceed 60 mL. Blood volumes are never to exceed 350 mL in 12 weeks.
15. Samples are collected prior to administration of REGN1908-1909.
16. On day 1, urine pregnancy test is completed prior to administration of REGN1908-1909 in women of childbearing potential. Postmenopausal women do not need urine pregnancy testing.
17. Total IgE and allergen-specific serum IgE levels (Fel d 2, Fel d 4, Fel d 7).
18. Genomic analysis is mandatory for all patients enrolling in the study. One DNA sample is to be collected on day 1/randomization, but if this sample collection was omitted at baseline, it can be collected at any subsequent visit. [REDACTED]
19. PK samples are drawn at any time in the outpatient visit day from day 8 through day 113 (end of study) visit.
20. After exiting the EEU, patients are monitored outside the EEU in an observation room for approximately 6 hours.
21. Patients will be observed for 6 hours in the observation room after receiving a single dose of REGN1908-1909 or placebo.
22. Blood draws should be performed before the EEU exposure
23. Cat EEU visit 3 and visit 6 must be spaced at least 3 weeks apart
24. Assessments and procedures at the unscheduled visit(s) are to be performed at the discretion of the principle investigator.
25. Screening visits 1 and 2 may be combined into 1 visit if the patient has a historical, positive cat SPT or cat IgE that was completed in the last 12 months.

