##### Laboratory Tests

Laboratory test results will be summarized by baseline and change from baseline to each scheduled assessment time with descriptive statistics.

Number and percentage of patients with a potentially clinically significant value (PCSV) at any post-randomization time point will be summarized for each clinical laboratory test.

Shift tables based on baseline normal/abnormal and other tabular and graphical methods may be used to present the results for laboratory tests of interest.

Listings will be provided with flags indicating the out-of-laboratory range values.

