## 10.6. Additional Statistical Data Handling Conventions

The following analysis and data conventions will be followed:

Definition of baseline:

The last assessment before the administration of study drug on day 1 will be considered as the baseline evaluation.

General rules for handling missing data:

- Rules for handling missing data for assessment (other than efficacy)
- If the start date of an AE or concomitant medication is incomplete or missing, it will be assumed to have occurred on or after the intake of study medication, except if an incomplete date (eg, month and year) clearly indicates that the event started prior to treatment. If the partial date indicates the same month or year of the intake of study medication date, then the start date by the study medication intake date will be imputed; otherwise, the missing day or month by the first day or the first month will be imputed.
- No imputations for missing laboratory data, ECG data, vital sign data, or physical examination data will be made for the purposes of safety analyses.

Visit windows:

- Assessments taken outside of protocol allowable windows will be displayed according to the case report form (CRF) assessment recorded by the investigator.

Unscheduled assessments:

- Extra assessments (laboratory data or vital signs associated with nonprotocol clinical visits or obtained in the course of investigating or managing AEs) will be included in listings and PCSV tabulations, but not summaries. If more than 1 laboratory value is available for a given visit, the first observation will be used in summaries and all observations will be presented in listings.

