5.7.3. Analysis of Vital Signs

Vital signs (temperature, pulse, blood pressure, and respiration rate, and oximetry) will be summarized by Baseline and change from Baseline to each scheduled assessment time with descriptive statistics. The graphs of mean (or median) value of some vital sign parameter vs. visit will also be plotted.

A summary of PCSVs will be constructed. Shift tables based on baseline normal/abnormal and other tabular and graphical methods may be used to present the results for laboratory test of interest.

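### SAP 6.6 leaves out the protocol's rule that extra laboratory and vital-sign values enter the PCSV tabulations, so by-arm counts of potentially clinically significant values could be too low

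*SAP*

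**What the plan says.** Both documents have a rule for assessments made outside the schedule.

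- **Protocol 10.6**: extra laboratory data and vital signs "will be included in listings and PCSV tabulations, but not summaries".
- **SAP 6.6**: the rule covers "laboratory data or vital signs associated with non-protocol clinical visits or obtained in the course of investigating or managing adverse events", and these values "will be included in listings, but not summaries except for the endpoint determination".

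Three other places bear on which values count towards a PCSV.

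- **Protocol 10.4.4.2, Laboratory Tests**: "Number and percentage of patients with a potentially clinically significant value (PCSV) at any post-randomization time point will be summarized for each clinical laboratory test".
- **SAP 5.7.3, Analysis of Vital Signs**: "A summary of PCSVs will be constructed". The next sentence of that section turns to laboratory tests. SAP 5.7.2 defines a treatment-emergent laboratory PCSV but does not say whether unscheduled values qualify.
- **SAP 6.5, Visit Windows**: the windows are built to leave no gaps, and under them "all available values obtained from unscheduled visits, early termination (ET) visit and end of treatment (EOT)/end of study (EOS) have the potential to be summarized".

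**The concern.** A PCSV count asks whether a patient crossed a threshold at any time after dosing. Values obtained because something was being investigated are among the most informative for that question. Protocol 8.1.3 gives repeat testing after abnormal laboratory results and follow-up of adverse events as reasons for unscheduled visits. If such values appear only in listings, a patient whose sole threshold crossing was found at an extra assessment is tabulated as having no PCSV.

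The stake is the by-arm safety table. The adverse event tables do not reliably fill the gap. Under Protocol 9.4.5 and SAP 4.6.1 an abnormal result becomes an adverse event only if it meets further criteria, such as symptoms or a need for intervention. The PCSV table is the threshold-based check that does not depend on that judgment.

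**Working it through.** No power, alpha or effect-size figure is involved and the plan states no number to reproduce. The check is a comparison of text, followed by a count of scheduled draws.

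**1. The two rules side by side.**

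| Destination of extra values | Protocol 10.6 | SAP 6.6 |
|---|---|---|
| Listings | included | included |
| PCSV tabulations | included | not mentioned |
| Summaries | excluded | excluded, except for endpoint determination |

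The SAP therefore differs in two ways: it does not name PCSV tabulations, and it adds an exception for endpoint determination.

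**2. Does the exception bring the values back?** The SAP does not define it. The sentence before it in 6.6 concerns how baseline and end-of-treatment values are determined, and the exception most naturally refers to those. It does not mention PCSVs.

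**3. Does another SAP section bring them back?** SAP 5.7 points to the PCSV thresholds in 10.3. SAP 5.7.2 says nothing on scheduled versus unscheduled values. SAP 5.7.3 calls the output a summary, which is the class of output that 6.6 closes to these values. SAP 6.5 leans the other way, but it governs data analyzed by visit, offers only the potential to be summarized, and does not name PCSVs. No section states that extra values enter the PCSV counts.

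**4. What the protocol requires.** For laboratory tests, 10.4.4.2 asks for patients with a "potentially clinically significant value (PCSV) at any post-randomization time point will be summarized for each clinical laboratory test". A count restricted to scheduled values does not meet that. For vital signs, 10.4.4.2 promises only descriptive statistics, so there the conflict is with 10.6 alone.

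**5. Where extra laboratory values matter most.** In Table 1 of Protocol 8.1, hematology and chemistry on Day 1 are drawn before dosing (footnote 15). The scheduled post-dose draws are on Days 29, 57, 85 and 113, with an early-termination visit for patients who withdraw. There is no such draw on Day 8, the day of the first post-dose challenge.

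- Nominal gap from dosing to the first scheduled draw: 29 − 1 = 28 days.
- With the ±2-day window on Day 29: (27 − 1) to (31 − 1) = 26 to 30 days.

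For a patient who stays on study, a hematology or chemistry result in that gap would ordinarily come from an extra assessment.

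**6. Scale.** With 30 patients planned per arm, one patient more or fewer with a given PCSV changes that arm's percentage by 1/30 = 3.3 percentage points. How many patients would be affected cannot be derived from the documents.

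**The case against.** The strongest reply is that the SAP omits the inclusion but does not forbid it. The protocol treats PCSV tabulations and summaries as different outputs, and 6.6 bars only summaries. SAP 5.7.2 defines a PCSV by a value after treatment without limiting it to visits, and ties only the descriptive statistics to scheduled times. SAP 6.5 wants windows that take in unscheduled values. On that reading the extra values still count. This stands as far as showing that the SAP is ambiguous. It does not settle the matter, because 5.7.3 calls the PCSV output a summary. Two programmers could produce different tables.

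A second reply is that nothing disappears: the values remain in listings, and Protocol 10.4.4.2 adds out-of-range flags to the laboratory listings. That is true, but a listing gives no by-arm count. Also, a repeat that confirms an abnormal scheduled value loses nothing, since the scheduled value already counts. The loss is confined to crossings seen only at an extra assessment.

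A reader might infer more than the documents support:

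- **That no laboratory abnormality before Day 29 could be counted.** An early-termination visit has its own draw, and the Day 29 window opens two days earlier.
- **That vital signs taken during challenge reactions are generally excluded, or that hypotension would fall between scheduled readings.** Expected asthmatic and allergic symptoms after exposure are not adverse events (Protocol 9.4.1, SAP 4.6.1), and footnote 12 of Table 1 already foresees additional readings at challenge visits. Many such readings are therefore not clearly within 6.6. Reactions beyond expected symptoms are reportable as adverse events, and readings from managing those are covered. Nothing in the documents says when hypotension would be recorded.
- **That the change list in SAP 1.2.3 shows an undeclared departure.** That list compares SAP versions, not the SAP with the protocol, so its silence is not evidence.

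**Conclusion.** The discrepancy is real. SAP 6.6 lacks the protocol's inclusion of extra laboratory and vital-sign values in PCSV tabulations, and no other SAP section clearly supplies it. Followed as written, 6.6 could produce by-arm PCSV counts that are too low against Protocol 10.6 and, for laboratory tests, incomplete against 10.4.4.2.

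This rests on two readings: that the PCSV output is a summary within the meaning of 6.6, as 5.7.3 words it, and that endpoint determination does not extend to PCSVs. An undercount is a possible consequence, not a certain one, and its size is unknown. It concerns descriptive safety tables only. The efficacy analyses and the adverse event incidence are unaffected.

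**What to change.** - **SAP 6.6**: restore the protocol's rule, so that extra laboratory and vital-sign assessments go into listings and PCSV tabulations and stay out of by-visit descriptive summaries. Say what endpoint determination covers.
- **SAP 5.7.2 and 5.7.3**: state that PCSV counts use all scheduled and unscheduled post-dose values. By-visit descriptive summaries stay as they are.
- **SAP 6.5**: reconcile with 6.6, so that it is clear which outputs unscheduled values may enter.

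The cost is one restored phrase in 6.6 and a clarifying line in each of the other sections, with no new data collection. PCSV counts may rise slightly.
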